6. Individuals who do not meet the criteria for participation in this study (screen failure) within the 6 week screening period may be rescreened.
7. Participants completing Treatment Period 1 will be randomized into switching or non-switching treatment arms in a 1:1 ratio prior to dosing on Week 10, stratified based on 3 weight groups (Week 10 weight). Participants randomized to the non-switching arm will continue on Humira for the remainder of the study, and participants randomized to the switching arm will continue switching in each TP (TP2: PF-06410293; TP3: Humira; TP4: PF-06410293).
8. Complete physical exam (PE) of major body systems. Additional targeted PE may be performed during the study at the investigator's discretion, as indicated by signs and symptoms of ongoing AEs.
9. Vital signs include blood pressure, respiratory and pulse rate, body temperature, body weight, with height measured at Screening only. Blood pressure and pulse rate should be taken from the participant in the supine position after the participant has been resting quietly for at least 5 minutes.
10. Body weight (BW) for Randomization should use the one collected at Week 10. Every effort should be made to obtain BW at Week 10 prior to randomization, however, if the Week 10 BW is not available, Screening or Baseline BW (whichever is closest to Week 10 visit) may be used to randomize.
11. Pregnancy testing at Screening in female participants of childbearing potential by central lab serum HCG test. Pregnancy testing (HCG) after Screening will be performed locally using urine samples. Pregnancy testing may be repeated more frequently if required by IRB/ECs or local regulations, or if potential pregnancy is suspected.
12. Blood samples should be collected for ADA and NAb testing at the time when PK samples are also collected and prior to the next investigational product administration.

CCI

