14. Please refer to [Table 1](#) (PK Sampling Table). **ALL PK samples will be collected prior to study dose (pre-dose)** at visits where onsite injection is scheduled. Blood samples for determination of adalimumab trough drug concentrations will be collected within 6 hours prior to the investigational product administration on Weeks 22, 24, 26, 28, and on Day 1 (time 0), Weeks 10 and 16 at a maximum of 48 hours prior to, but as close as possible prior to the next investigational product administration (ie, pre-dose). The 2-week PK sampling period starts with Week 30 predose PK collection and ends with Week 32 predose PK collection. Blood samples for determination of adalimumab drug concentrations for the 2-week PK profile will be collected starting with the Week 30 injection of investigational product (PK Profile Day 1): blood will be collected within 6 hours prior to investigational product administration. For the subsequent PK Profile Days, post-Week 30 dosing times for serum collections are 48 ( $\pm 4$ ) hrs on PK Profile Day 3, 72 ( $\pm 6$ ) hrs on PK Profile Day 4, 96 ( $\pm 8$ ) hrs on PK Profile Day 5, 144 ( $\pm 8$ ) hrs on PK Profile Day 7, 240 ( $\pm 24$ ) hrs on PK Profile Day 11, and 336 ( $\pm 24$ ) hrs on PK Profile Day 15. **Every effort should be made to draw samples within the scheduled time points.** The 2-week PK Profile collections may be completed using home health care service.
15. Investigational product will be administered by the participant, care giver or site personnel every other week using pre-filled syringes provided by the sponsor; on-site injections will occur during every scheduled visits after PK and ADA/NAb sample collection. The first SC injection should be administered by the participant while at the clinic under the supervision of the site's investigator or designee. Any issues may be reviewed at that time. The first injection must be an abdominal injection. Subsequently, the injection location may be the abdomen or upper front of either thigh. The first TP4 injection at Week 22 and injections at Weeks 24, 26, 28 and 30 (before starting the PK profile) must also be administered in the abdomen under the supervision of the site's investigator or designee. Applicable injection details (eg, date) will be recorded in the electronic Participant Dosing Log. Investigational product will be dispensed to the participant at each visit.

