##### **9.4.3.2. ADA and NAb Analysis**

For the ADA and NAb data, the percentage of participants with positive ADA and NAb will be calculated and summarized for the safety-randomized population by each visit in Treatment Periods. For participants with positive ADA and NAb, the magnitude (titer), time of onset, and duration of ADA and NAb response will also be described. In addition, the impact of ADA and NAb on PK over time will be assessed for each treatment arm.

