#### 6.2.2. Anti-drug antibody (ADA) and Neutralizing Anti-Drug Antibody (NAb) Results

For the ADA and NAb data, the percentage of participants with positive ADA and NAb will be calculated and summarized for the Safety-Randomized population by each visit for TP1 through TP4. The magnitude (titer) and time of first positive sample will also be described.

ADA and NAb status at the end of study will be used to characterize the participants response as either persistent or transient. For participants with at least one ADA/NAb positive sample, persistent response is defined as ADA/NAb positive at the last sample, and transient response is defined as having had at least one ADA/NAb positive sample, and an ADA/NAb negative at last sample.

In addition, the impact of ADA and NAb on PK over time will be assessed as specified in section 6.1.1 and 6.2.1.

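### The SAP labels ADA/NAb responses persistent or transient from the last sample alone, and omits the duration summary that the protocol specifies

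*SAP*

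**What the plan says.** SAP 6.2.2 announces the basis of the classification: "ADA and NAb status at the end of study will be used to characterize the participants response as either persistent or transient". Among those who test positive at some visit, the first label is assigned as follows: "persistent response is defined as ADA/NAb positive at the last sample". Everyone else who was ever positive, and whose final result is negative, is called transient. The section sets no minimum number of positive samples and no minimum length of response. It has no separate category for a participant whose first positive is also the last sample.

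Besides the percentage positive at each visit, the SAP plans this: "The magnitude (titer) and time of first positive sample will also be described". It neither defines nor summarises duration, in 6.2.2 or in any other section.

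Protocol 9.4.3.2 goes further. For participants with a positive result, "the magnitude (titer), time of onset, and duration of ADA and NAb response will also be described". The protocol synopsis makes the same commitment under Immunogenicity.

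The SAP's summary of changes (Section 1, Table 1) records 6.2.2 only as updated with more detail. A separate entry lists analyses that were taken out, and duration of the antibody response is not among them.

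**The concern.** The words persistent and transient describe how long a response lasts. The rule that assigns them looks at one time point and ignores everything before it, apart from requiring some positive sample. A brief response caught at the end receives the label for a durable one, and a long response that has just cleared receives the label for a short one.

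For participants who stop early, the last sample is the early-termination sample or whatever was last available. Their label therefore also depends on when follow-up ended.

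Immunogenicity in the two arms is a stated secondary objective of a trial meant to support interchangeability. A table of persistent and transient responders by arm will be read as a comparison of durability, which the rule does not measure. The one planned output that would have measured it, the protocol's duration summary, is absent from the SAP, and nothing in the change table tells a reader so.

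**Working it through.** The plan gives no sample size, power or error rate for this point, so there is no stated figure to reproduce. The check applies the SAP rule literally to the sampling schedule.

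**Inputs**
- Sampling weeks. Footnote 12 to the protocol Schedule of Activities ties antibody sampling to PK sampling: "Blood samples should be collected for ADA and NAb testing at the time when PK samples are also collected". Footnote 14 gives the predose weeks before the PK profile: "Weeks 22, 24, 26, 28, and on Day 1 (time 0), Weeks 10 and 16". The antibody row of the schedule marks Weeks 0, 10, 16, 22, 24, 26, 28, 30 and 32, which is 9 samples.
- Rule (SAP 6.2.2). Any positive sample and the last sample positive: persistent. Any positive sample and the last sample negative: transient.
- Observed span = week of last positive sample − week of first positive sample.

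**Two participants, both possible on this schedule**
- Case A: negative through Week 30, positive at Week 32. One positive sample, span 32 − 32 = 0 weeks. SAP label: persistent.
- Case B: positive at Weeks 10, 16, 22, 24, 26, 28 and 30, negative at Week 32. Seven consecutive positive samples, span 30 − 10 = 20 weeks. SAP label: transient.

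**All patterns for a participant sampled through Week 32**
- Not positive at Week 0: eight samples remain, giving 2^8 − 1 = 255 patterns with at least one positive. Of these, 2^7 = 128 are persistent and 2^7 − 1 = 127 are transient.
  - Persistent spans run from 0 to 32 − 10 = 22 weeks.
  - Transient spans run from 0 to 30 − 10 = 20 weeks.
- Allowing a positive at Week 0, which the rule does not exclude: persistent spans run from 0 to 32 weeks and transient spans from 0 to 30 weeks.

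The two labels cover almost the same range of spans. Case B is the longest post-baseline span that the rule can call transient. The pattern counts show what the rule permits; they do not show how often each pattern will occur.

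**Does a span-based rule sort the two cases differently?** Take persistent to mean a span of at least T weeks. With T = 8, 12, 16 and 20 (assumed values, none from the documents), Case A (0 weeks) becomes transient and Case B (20 weeks) becomes persistent at every T.

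**Limit of a duration measure.** Observed span is cut off at Week 32. A response first seen at Week 24, the first sample after the Week 22 switch, can show at most 32 − 24 = 8 weeks, and one first seen at Week 32 shows 0. A duration summary therefore has to mark responses that are still positive at the last sample.

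**The case against.** The strongest defence is that nothing downstream uses the label.
- The interchangeability decision rests only on the 90% confidence intervals for Cmax and AUCtau.
- The PK summaries by antibody status use Week 30 or the corresponding visit (SAP 6.1.1 and 6.2.1), and the immunogenic safety summary uses antibody status in TP1 (SAP 6.6.1.2.1).
- The secondary endpoint is the percentage positive and titers over time, and both remain planned, as does time of first positive.
- The rule is explicit, reproducible and identical in both arms.
- The SAP reserves the right to modify the protocol's plans, and only major changes to the primary endpoint or its analysis call for an amendment.

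All of this stands, and it confines the point to one descriptive table. It does not make the label measure duration. Percentage positive by visit is a group figure and does not show how long any one participant's response lasted.

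Three stronger readings are tempting, and the documents do not support them.
- A reader might infer that the rule inflates persistence in the switching arm because the last switch is at Week 22. That arm first receives PF-06410293 at Week 10, so a switch-related response could appear from the Week 16 sample onward. The documents give no onset data by arm.
- A reader might put a number on the participants mislabelled. No antibody rate or distribution of onset is given. Half of the 314 evaluable participants (157 per arm) would also be the wrong denominator: these analyses use the Safety-Randomized population, whose size is not stated.
- A reader might infer that dropping duration breaches the protocol. The SAP may make such a change; the fault is that the change is not declared or explained.

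**Conclusion.** The point holds for a descriptive secondary immunogenicity summary. The SAP's labels do not track persistence: one positive sample can earn the durable label, seven over 20 weeks can earn the short-lived one, and the post-baseline spans under the two labels (0–22 and 0–20 weeks) nearly coincide. The protocol's duration description has been lost without notice in the change table.

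The conclusion rests on a literal reading of SAP 6.2.2 and on the nine scheduled samples; no assumed rate enters it. The primary conclusion is untouched. How many participants would be labelled misleadingly, and whether the arms would differ in this, cannot be derived from the documents. The change is worth making because the output bears on a secondary objective and the correction is cheap.

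**What to change.** - Restore to SAP 6.2.2 a summary by arm of the duration of ADA and NAb response, in weeks from first to last positive sample, as protocol 9.4.3.2 intends. Flag responses still positive at the last sample as ongoing (censored), and show how many samples were available after first positivity.
- If the persistent and transient labels are kept, base them on the span or the number of positive samples, with a threshold that the sponsor pre-specifies. Requiring only that the last two samples be positive would not be enough: Case B would still not count as persistent, and a participant positive only at Weeks 30 and 32 (span 2 weeks) would.
- Report participants whose first positive is their last sample, including at early termination, as a separate indeterminate category.
- Record the change in the SAP's summary of changes.

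The cost is SAP wording and minor reprogramming from data already collected. The downside is one extra category, which makes the remaining groups slightly smaller.

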### **6.2.3. Safety endpoints**

The analyses and summary for safety endpoints is provided in Section 6.6.

### **6.3. Other Endpoint(s)**

The summary for other endpoints including demographic and baseline characteristic, study drug administration is provided in section 6.5.

### **6.4. Subset Analyses**

PK data over time will be assessed by ADA and NAb status. Please see the details in Section 6.1.1 and 6.2.1.

### **6.5. Baseline and Other Summaries and Analyses**

#### **6.5.1. Participant disposition**

Participant disposition will be summarized for enrolled population and ITT-Randomized population and will include the number and percentage of participants enrolled, randomized, treated, status, reason/description and other relevant data.

#### **6.5.2. Participant demographics, Baseline characteristics**

Demographics and baseline characteristics (age, sex, height, weight, race, ethnicity, etc.) will be summarized descriptively using Enrolled population, , ITT- Randomized population, and PK population.

#### **6.5.3. Study Treatment Exposure**

Study drug exposure (total number of doses, duration of treatment, total number of participants with any missed doses, etc.) will be summarized descriptively using Safety-TP1 population by Humira arm and Safety-Randomized population by switching arm and non-switching arm.

#### **6.5.4. Concomitant Medications and Nondrug Treatments**

Collected prior and concomitant medications will be coded by WHO medical dictionary; participants who received these medications will be summarized using Safety-Randomized population from TP2 to TP4 by switching arm and non-switching arm.

## **6.6. Safety Summaries and Analyses.**

Unless otherwise specified, safety analyses for TP1 will be performed using the Safety-TP1 population for the Humira arm. Safety analyses for TP2 and beyond will be performed using Safety-Randomized populations by switching arm and non-switching arm.

### **6.6.1. Adverse Events**

Adverse events will be classified using the medical dictionary for regulatory activities (MedDRA) classification system.

Unless otherwise specified, AE analyses for TP1 will be performed using the Safety-TP1 population for the Humira arm. AE analyses for TP2 and beyond will be performed using Safety-Randomized populations by switching arm and non-switching arm. Treatment-emergent adverse events definitions for TP1 and TP2 and beyond are provided in section 3.5.1.

#### **6.6.1.1. Adverse Event for TP1**

Adverse events (including overall summary of treatment-emergent adverse events; treatment-related adverse events; adverse events classified as Grade 3 or higher; adverse event leading to discontinuation; and SAEs) will be summarized for the Humira arm. All-causality TEAE and SAE will be also summarized by body system and preferred term according to MedDRA terminology.

#### **6.6.1.2. Adverse Event for TP2 and Beyond**

Adverse events (including overall summary of treatment-emergent adverse events; treatment-related adverse events; adverse events classified as Grade 3 or higher; adverse event leading to discontinuation; and SAEs, etc.) will be summarized by switching arm and non-switching arm. All-causality TEAE and SAE will be also summarized by body system and preferred term according to MedDRA terminology.

AESI will be summarized by body system and preferred term according to MedDRA terminology and also by AESI categories, subcategories and preferred term.

##### **6.6.1.2.1. Effect of Immunogenicity on Safety**

Immunogenic adverse effect during TP2 and beyond will be summarized for 2 subgroups of safety-randomized population: ADA positive in TP1 and ADA negative in TP1 subgroups (if applicable):

- Percentage of participants with ISR AEs (as per the investigators)
- Percentage of participants with medically evaluated AEs that meet Sampson's Criteria
- Percentage of participants with medically evaluated potential Hypersensitivity, Angioedema, Anaphylaxis, Cytokine Storm, and Delayed immune responses

The identification of participants with AEs that meet Sampson criteria and the statistical summary will be provided in a supplemental statistical specification.

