### Immunogenicity

For the ADA (antidrug antibodies) and NAb (neutralizing antibodies) data, the percentage of participants with positive ADA and NAb will be summarized for the safety-randomized population by each visit in each Treatment Period. For participants with positive ADA and NAb, the magnitude (titer), time of onset, and duration of ADA and NAb response will also be described. In addition, immune-related safety will be described for the safety population including injection site reactions (ISR), hypersensitivity, anaphylaxis, and angioedema.

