### **6.3. Measures to Minimize Bias: Randomization and Blinding**

This is an open-label study.

Upon successful completion of TP1, participants will be randomized (1:1 ratio) into either the switching arm (ie, to PF-06410293) or the non-switching arm (ie, continue to receive Humira). Randomization will be stratified by 3 body weight groups ( $\geq 40$  kg to  $< 70$  kg;  $\geq 70$  kg to  $< 100$  kg;  $\geq 100$  kg to  $\leq 130$  kg). Participants randomized to the Humira arm will continue on Humira for the remainder of the study, and participants randomized to switch to PF-06410293 will continue switching in each TP (TP2: PF-06410293; TP3: Humira; TP4: PF-06410293).

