### **6.3.2. Breaking the Blind (Not Applicable)**

This is an open-label trial.

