##### **9.4.2.1. Adverse Event**

Adverse events will be classified using the medical dictionary for regulatory activities (MedDRA) classification system.

Adverse events (treatment-emergent adverse events; treatment-related adverse events; adverse events classified as Grade 3 or higher; and SAEs) will be summarized by body system and preferred term according to MedDRA terminology. A treatment-emergent adverse event (TEAE) is defined as any adverse event that occurs after the beginning of the study treatment.

Adverse events of special interest including opportunistic infections and immune-based adverse effects will be summarized using grouped Medical dictionary for regulatory activities (MedDRA) codes in addition to presentation of individual AE preferred terms.

Immune-based adverse effects may be both acute and delayed and include injection-site reactions (ISRs), AEs that fulfill Sampson Criteria, and AEs identified as potential hypersensitivity/anaphylactic reactions using a System Medical Dictionary for Drug Regulatory Activities (MedDRA) standardized MedDRA query (SMQ) that occur in relation to the administration of the study drug. Adverse events recorded on the CRF as ISRs will be summarized both as individual event symptoms and as a group for the purpose of comparing the overall incidence of ISRs. Therefore, the following safety endpoints will be summarized for all participants, and for ADA positive and negative subgroups:

- Participants with ISRs (as per the investigators);
- Participants with AEs that fulfill Sampson's Criteria;
- Participants with AEs belonging to SMQ broad groupings of potential hypersensitivity / anaphylactic reactions.

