### 3.5. Safety Endpoints

#### 3.5.1. Adverse Events

A treatment-emergent adverse event (TEAE) for TP1 summary is defined as any adverse event that occurs after the beginning of the study treatment in TP1 and before the first dose of investigational product administered after randomization in TP2.

A treatment-emergent adverse event (TEAE) for TP2 to TP4 summary is defined as any adverse event that occurs after the first dose of investigational product administered after randomization in TP2. Adverse events of special interest (AESI) include Targeted medical events (TME) which are defined for Adalimumab biosimilar program and are maintained in a list in the product's Safety Review Plan.

Immunogenic adverse effects include injection-site reactions (ISRs); medically evaluated AEs that meet Sampson Criteria, and medically evaluated AEs identified by broad MedDRA SMQ for Hypersensitivity/Anaphylaxis /Angioedema; medically evaluated AEs identified as potential Cytokine storm, and medically evaluated AEs identified as potential Delayed immune responses.

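### SAP 6.6.1.2.1 does not list the protocol's all-participants immune-reaction summary or its unfiltered broad-SMQ count, and leaves the added medical evaluation undefined in an open-label trial

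*SAP*

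**What the plan says.** Protocol 9.4.2.1 introduces its immune-based measures with the rule that "the following safety endpoints will be summarized for all participants, and for ADA positive and negative subgroups". It then names three: injection-site reactions as the investigator reports them, events fulfilling Sampson's criteria, and "Participants with AEs belonging to SMQ broad groupings of potential hypersensitivity / anaphylactic reactions". The synopsis (Protocol 1.1, Immunogenicity) agrees on the population: "immune-related safety will be described for the safety population including injection site reactions (ISR), hypersensitivity, anaphylaxis, and angioedema". Protocol 9.4.2 presents safety for TP2 to TP4 by arm.

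SAP 3.5.1 keeps the broad SMQ as the way events are found but adds a step: the category becomes "medically evaluated AEs identified by broad MedDRA SMQ for Hypersensitivity/Anaphylaxis /Angioedema". Sampson events receive the same qualifier, and two categories are new: "medically evaluated AEs identified as potential Cytokine storm, and medically evaluated AEs identified as potential Delayed immune responses".

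SAP 6.6.1.2.1 then sets out the tables: injection-site reactions per the investigator, evaluated Sampson events, and "Percentage of participants with medically evaluated potential Hypersensitivity, Angioedema, Anaphylaxis, Cytokine Storm, and Delayed immune responses". It gives them for two subgroups of the Safety-Randomized population, defined by antibody status in TP1. Its last sentence sends the identification of Sampson events, and the statistical summary, to a supplemental specification.

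On masking, Protocol 6.3 says: "This is an open-label study".

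**The concern.** Safety and immunogenicity after switching are secondary objectives, and these tables carry no test, so the definition of a counted event largely determines the result. Two things changed between the documents. The SMQ measure went from any participant with a coded event to a participant with an evaluated one, and neither document says who evaluates, by what criteria, whether that person can see the arm, or what happens to events judged not to qualify. The summary of all randomised participants was also not carried over.

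If the evaluation were more lenient in one arm than in the other, it could create or hide a difference. The table against which a reader would check this, the unfiltered count by arm, is not listed.

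**Working it through.** The plan has no figure on this point: neither document gives an immune-reaction rate or a target difference. The check is mainly a comparison of texts.

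**1. Side by side**

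| Item | Protocol 9.4.2.1 | SAP 3.5.1 and 6.6.1.2.1 |
|---|---|---|
| Injection-site reactions | Per investigator | Per investigator (unchanged) |
| Sampson events | Events fulfilling the criteria | Same, after medical evaluation |
| Hypersensitivity/anaphylaxis | Any event in the broad SMQ grouping | Broad SMQ as screen, then medical evaluation; angioedema named |
| Cytokine storm, delayed responses | Not listed | Added, after medical evaluation |
| Participants summarised | All, plus antibody positive and negative | Antibody positive in TP1 and negative in TP1 only |
| Evaluator, criteria, masking | No evaluation step | Not stated |

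The SAP does set such a safeguard elsewhere. Its section 4 requires PK-population decisions to be independent of PK results and final before database release. Immune-event classification has no counterpart.

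**2. What other tables can recover.** SAP 6.6.1.2 keeps all-causality TEAEs and SAEs by arm, body system and preferred term, so the coded terms stay visible. They do not give the number of participants with at least one SMQ event. One participant can have several terms in several body systems, so that number lies anywhere between the largest single row and the sum of the rows.

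**3. What the TP1 subgroups can show.** TP1 ends with the Week 10 pre-dose assessments and all participants receive Humira until then. Per the Schedule of Activities, the antibody samples in TP1 are on Day 1 and at Week 10. Randomisation and the first switch follow. A participant who first becomes positive after a switch is therefore classed as negative in TP1. SAP 6.2.2 reports antibody status by visit through TP4, but 6.6.1.2.1 does not link that later status to reactions.

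**4. Illustration, with assumed rates.** Inputs from the plan: 314 evaluable and at most about 420 enrolled, 1:1, so 314/2 = 157 to 420/2 = 210 per arm (the upper figure counts participants enrolled before randomisation). Assumed: the same coded SMQ rate p in both arms, with proportions 0.5 and 0.8 of flagged participants retained.

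Reported difference = p × (0.5 − 0.8):
- p = 5%: −1.5 points
- p = 10%: −3.0 points
- p = 15%: −4.5 points

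Counts at p = 10%:
- 157 per arm: 157 × 0.10 × 0.5 = 7.85 and 157 × 0.10 × 0.8 = 12.56, about 8 versus 13
- 210 per arm: 10.5 and 16.8, about 11 versus 17

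The effect can also run the other way. Coded rates of 10% and 15%, retained at 60% and 40%, both become 6.0%, which hides a 5-point difference. With equal retention and equal coded rates the difference stays 0.

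**The case against.** Several stronger readings are tempting, and the documents do not support them.

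- A reader might infer that the sponsor decides which reactions count. No evaluator is named; it could be the investigator, the sponsor or an independent masked reviewer.
- A reader might infer that the protocol's measures needed no judgement. At most the SMQ row comes close, and the protocol's introductory sentence limits it to events connected with giving the study drug. Sampson's criteria must always be applied case by case, and injection-site reactions are the investigator's report in both documents.
- A reader might infer that the evaluation can only remove events. That is plausible for the SMQ component. The same row also counts cytokine storm and delayed responses, which the SAP ties to no SMQ, so participants could be added. The SAP keeps the word potential and does not say that rejected events are dropped.
- A reader might infer that the raw data are hidden. The preferred-term tables by arm remain.

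Other points on that side also carry weight. The supplemental specification is not among the documents and may define the evaluation and further tables. If the subgroup tables are split by arm and every participant has a TP1 status, adding the two subgroups gives an all-participants evaluated count. Both documents allow the SAP to modify analyses other than major changes to the primary endpoint. Investigators who know the arm report the events, so masking the evaluator removes only part of the possible influence. Nothing in the documents suggests that retention would differ between arms.

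What remains is that the SAP as written lists neither the all-participants comparison nor the unfiltered SMQ count. No listed table restores the latter, and no safeguard on the evaluation is stated.

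**Conclusion.** The point holds as a gap between protocol and SAP that is cheap to close. It does not show bias. Following SAP 6.6.1.2.1 as written would omit a summary that Protocol 9.4.2.1 promises, would replace the broad-SMQ count with one that depends on an undefined evaluation, and would present both evaluated measures only in subgroups fixed before randomisation.

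The consequence is limited. These are descriptive secondary safety tables, and the decision rule rests only on the 90% confidence intervals for Cmax and AUCτ, which are unaffected. The size cannot be estimated from the documents. The 1.5 to 4.5 points above rest entirely on assumed event rates and assumed unequal retention. The conclusion also assumes that the supplemental specification does not already supply the missing table and masking; if it does, a cross-reference in the SAP would settle most of the point.

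**What to change.** In SAP 6.6.1.2.1, with matching wording in 3.5.1:

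1. Add a table by arm for all Safety-Randomized participants with investigator-reported injection-site reactions, Sampson-criteria events and the unfiltered broad-SMQ count. Show the medically evaluated counts beside it and keep the TP1 subgroup tables.
2. State who performs the medical evaluation, by what criteria, and what happens to events judged not to qualify. Have it done from a listing without arm, product, treatment-period label and ADA/NAb results, with classifications fixed before database release.
3. Reconcile whether immune-based effects belong to AESI. Protocol 9.4.2.1 includes them; SAP 3.5.1 points to a list kept in the Safety Review Plan. Until this is settled, it is unclear whether the by-period tables in SAP 6.6.1.2.2 cover them.

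The cost is SAP wording, one stripped listing and a few extra tables, with no new data. The evaluator sees less context, although event timing relative to the last injection can still be shown.
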